### **9.3 Exploratory analyses**

Exploratory analysis of intervention effectiveness across subgroups, and analysis of potential mediators of persistence in PrEP care across both study arms

Heterogeneity of the intervention effects across subgroups, including those stratified upon (city, age), and socioeconomic indicators, using unadjusted proportion tests and subgroups\*intervention arm interaction variables in GLMM models. We will examine expected mediators of primary and secondary study outcomes. Possible mediators are variables hypothesized to be on the causal pathway between the intervention and study outcomes (e.g. medication adherence self-efficacy, perceived benefits of PrEP, perceived ease of use of PrEP). For participants who seroconvert during the study, we will analyze levels of TFV-DP, PrEP persistence, and other clinically-relevant study data.

### **9.4 Mathematical modeling**

Mathematical modeling will be used to estimate the potential impact of scaling-up PrEP@Home for MSM across the United States. This will be done by using a robust model that simulates HIV transmission across dynamic sexual partnership networks, which we have used to predict the impact and efficiency of CDC's PrEP guidelines for MSM. Model parameters related to PrEP persistence and adherence will be based on the efficacy results in Aims 1-2.1. Sensitivity analyses will vary levels of and heterogeneity in PrEP access, PrEP@Home uptake, and time-varying PrEP adherence. The aim of these models will be to address the question of how PrEP@Home could reduce HIV incidence in the population by improving persistence above levels currently observed in clinic-based PrEP demonstration projects. Modeling activities will also include extending our web-based PrEP forecasting tool for public health policymakers (<https://prism.shinyapps.io/cdcprep-guidelines>) to incorporate new parameter data and sensitivity analyses. Model outputs such as the cumulative number of infections averted (a measure of impact) and the number needed to treat to prevent one new infection (a measure of efficiency) will be fed into the cost-effectiveness analyses (Aim 3) as input parameters.

### **9.5 Qualitative**

Interviews and survey assessments among clinicians, healthcare managers, and patients involved in PrEP care to inform roll out of home care, should the intervention demonstrate efficacy. Qualitative interviews will be conducted with approximately 40 participants.

To inform future research with the PrEP home care system and to contextualize study results, we will conduct in-depth interviews (IDI) and key informant interviews (KII).

**IDI:** Interviews will seek to explore the experiences of home care users and standard of care participants over time. We will use a timeline, activity-based approach, prompting participant memories and creating an interactive discussion between moderator and participant regarding PrEP care experiences. PrEP care visits will be plotted on the timeline, with participants adding surrounding life and PrEP care-related events. IDI topics will include: (1) barriers and facilitators to PrEP care, (2) problems with and benefits of the home care or standard of care, (3) ways to address problems and amplify success of home care or standard of care, and (4) factors that influence successful persistence in or fall-off from PrEP care. IDI will be conducted until data saturation has been reached. Purposive sampling of study participants will include up to 15 IDI with participants maintained in PrEP care (10 intervention, 5 control) and up to 15 IDI with participants not maintained in PrEP care (10 intervention, 5 control). PrEP care is a new and dynamic field, and broader healthcare system changes also may occur, so we anticipate that conducting this qualitative exploration among intervention and control participants is warranted. Participants who seroconvert during the study will also be asked to participate in IDI to assess their experience using PrEP and follow-up care, including app use, during their time on the study.

**Stigma IDI:** In addition to the interviews which will explore the experiences of home care users and standard of care participants over time, a second set of IDI will be conducted. In August 2020, the PrEP@Home parent grant was awarded a minority research supplement, which will allow a junior faculty-level scientist, [name] with Family Health International (FHI 360), to conduct research as part of PrEP @Home. This supplemental qualitative research seeks to explore the relationship of stigma and resilience, and their role as potential barriers and facilitators to healthcare engagement among men who have sex with men (MSM). Interviews will be via ZOOM, given the current social distancing measures required for continuation of the study and to protect participants. Interviews will explore sexual and PrEP stigma, individual, social, and neighborhood/community level access to resilience resources, and the role of these factors as barriers and facilitators of PrEP@Home and healthcare engagement. Because some individuals may not develop resilience to sexual stigma and/or PrEP stigma, and others do even with lower levels of PrEP stigma and sexual stigma, qualitative inquiry will be critical in exploring these constructs among both White MSM and MSM of color. IDI will be conducted with participants after their 6-month visits by ZOOM, and should not take longer than 60 minutes. Participants will be paid \$60 for their participation. Participants in the parent study who agreed to be contacted for future research will be recruited for interviews. Approximately six interviews will be conducted per site (i.e., four in intervention, three in control). At least two-thirds of participants will be MSM of color, and at least half will be ages 18 to 34 (informed by the parent grant's sampling frame; N=up to 25 interviews total).

**Injectable PrEP IDI:** In addition to the interviews which will explore the relationship of stigma and resilience in healthcare engagement, a third set of IDI will be conducted. In December 2020, the FDA approved a new injectable medication for PrEP called cabotegravir. It works for PrEP just like Truvada® or Descovy®. The difference is that it's given intramuscularly (in the buttocks) every 2 months instead of taking a daily pill. We are preparing a new project where we would integrate the administration of this medication into the PrEP@Home model. In other words, we would come to participant's homes to give them their shots every 2 months and we would also draw blood. This qualitative research seeks to explore PrEP@Home participant's opinions and preferences regarding home-based injectable PrEP to inform our future study. We are not adding the at-home injectable PrEP to this study, but only conducting interviews to assess subjects' opinions on it. Interviews will be via ZOOM, given the current social distancing measures required for continuation of the study and to protect participants. Each IDI should not take longer than 30 minutes. Participants will be paid \$75 for their participation. Participants in

PrEP@Home who are currently enrolled at the Emory site and between the ages of 18 and 29 will be recruited for interviews. Approximately fourteen interviews will be conducted.

**KII:** Key informant interviews will be conducted with the intervention and standard of care control clinicians (n=6), as well as PrEP-prescribing clinicians and managers at institutions interested in scaling up PrEP (n=20). For the three intervention clinicians (one per site) and three comparable standard of care clinicians, KII will explore the experience of providing PrEP care to participants over the course of the clinical trial, focusing on areas for potential improvement of PrEP@Home or standard of care provision. KII with members of up to 10 institutions interested in scaling up PrEP will focus on how scale-up of PrEP@Home would influence their institution, and exploring desired/required adaptations of the system for each care setting. This set of KII will sample from PrEP care settings such as: STI/county public health clinics, Health Maintenance Organization (HMO), hospital teaching clinics, and Federally Qualified Health Centers. Depending on data saturation, we will conduct up to 20 interviews with members of these care settings, half with clinicians and half with managers at these institutions. KII will include a briefing regarding the home care system, and the results of the clinical trial. The interviews will then explore: (1) How would expanding PrEP home care impact each system of care provision, (2) What are areas of the system that would need to be adapted or developed, and (3) how home care can best be leveraged in their setting to promote their institution's goal of scaling up PrEP.

*Analysis for IDI and KII:* Transcriptions and interviewer notes will be entered into maxQDA qualitative software to facilitate data management and analysis. Analysis of the data will be led by MPI [REDACTED] and will begin with classification efforts to code data, conducted concurrently with data collection, in line with the constant comparison analysis method. This method leverages the ability of qualitative research to quickly identify main themes, and then explore them in further depth among subsequent participants. To ensure consistency, coding will be verified by multiple study members trained in analysis. Final analysis will compare data within and across codes and themes, developing theoretical models based on grounded theory principles to answer study questions regarding PrEP@Home adaptation, scale-up considerations, and future research directions.

In-depth interviews will be conducted during and after the trial using either telephone or videobased systems and will be facilitated by Emory University.

## **9.6 Cost-effectiveness and cost-utility analyses**

We will conduct an economic analysis from both the payer perspective (the cost to the party implementing the program) and societal perspective (the payer costs plus the cost to the participant for participating in the program) to estimate the cost, cost-effectiveness, and cost-utility of the intervention relative to standard of care. Including the societal perspective accounts for costs to all parties, acknowledges the value of competing uses for societies' resources, and maximizes comparability with other cost-effectiveness analyses. The cost analysis will calculate the overall cost of implementing the program, the cost per participant, and the cost per person contacted.

### **9.6.1 Costing the intervention and standard of care arms**

Comprehensive cost analysis will be conducted to assess the cost of developing and implementing the PrEP@Home intervention. A micro-costing approach will be used along with the standard literature practice of itemizing the intervention components and attaching a dollar value to them. Two categories of costs will be defined: *developmental costs* (the initial or start-up

costs involving the time spent in developing the intervention) and *implementation costs* (on-going costs of delivering the intervention). The development costs will include costs from the first phase of the research including salaries and fringe benefits for intervention development staff, pilot testing of the intervention, study recruitment, screening, consenting, enrollment, and mailing systems; and piloting lab procedures. Implementation costs will include recruitment, salary and fringe benefits for an intervention coordinator, kit component, production and laboratory testing costs, drug costs (not paid by the study), and the as-needed cost of consultants and technical support, self-reported time participants spend adhering to the PrEP@Home intervention or standard of care, data management, and clinical costs. Participant's self-reported time spent involved in study activities will be translated into an opportunity cost, where participation incentives will be taken as a proxy of the cost of patient time and we will also use income data from study participants.

Costing analysis for the standard of care arm within the cost-effectiveness analysis will be based on secondary literature estimating the health care and societal costs associated with PrEP for MSM in the US. To calculate personnel costs, we will multiply these hours by wage rates gathered from the Bureau of Labor Statistics and calculate an average cost per man receiving care in the standard of care arm. We will carefully track these ongoing costs during the 12 months of implementation (the time period of the analysis) using standardized data collection tools. Cost data will be collected by extraction from accounting records, budget records, external contracts, study case report forms, PrEP prescription receipt data; interviews with program implementers; and self-report from participants. Data will be entered into a standardized excel spreadsheet with embedded formulas to calculate the cost. These methods have been used by our research team for economic analyses for a variety of HIV prevention interventions including PrEP interventions. Costs will be discounted at an annual rate of 3%.

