### **9.6.3 Cost-effectiveness and cost-utility analysis**

First, we will calculate the incremental cost-effectiveness ratio (ICER) for the intervention overall compared to standard of care as:  $[(\text{CostIntervention} - \text{CostStandardofCare})] / [(\text{Infections AvertedIntervention} - \text{Infections AvertedStandardofCare})]$ . This value will give us the cost per HIV infection averted. We will use bootstrapping to calculate the confidence interval around this ratio. If we let  $\Delta X$  denote the total number of infections averted by the intervention relative to standard of care, the corresponding savings in averted HIV-related treatment costs equals  $T * \Delta X$ , where  $T$  is the (discounted at an annual rate of 3%) lifetime cost of medical care averted each time an incident HIV infection is averted. Thus, the net cost of the intervention can be calculated as  $C - T * \Delta X$ , where  $C$  is total costs. Similarly, the total number of QALYs saved by the intervention equals  $Q * \Delta X$ , where  $Q$  is the number (discounted at an annual rate of 3%) of QALYs saved by preventing a single HIV infection. Estimates of  $T$  and  $Q$  are available in the literature. We will use the most up-to-date values available for our analyses (current estimates of  $T$  are \$330,000 and  $Q$

are 5.83). The cost-utility ratio (the net cost per QALY saved) is thus  $(C - T^* \Delta X) / Q^* \Delta X$ . The intervention will be considered “cost-saving” if the net cost per QALY saved is negative. The intervention will be considered “cost-effective” if the cost-utility ratio is less than commonly-cited U.S. thresholds (e.g., \$100,000 per QALY saved). One-way sensitivity analyses will be performed for all input variables to determine which inputs the cost-effectiveness and cost-utility estimates are most sensitive to. We will explore implementation scenarios including the impact of generic drug pricing, one of the major determinants of PrEP cost-effectiveness.

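### The ICER subtracts literature-based standard-of-care costs from micro-costed PrEP@Home costs with no common items, unit prices or price year, so it can partly reflect the cost source

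*Combined protocol and SAP*

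**What the plan says.** Section 9.6.1 sets out the intervention costing: "A micro-costing approach will be used along with the standard literature practice of itemizing the intervention components". It defines two cost categories. Developmental costs include staff salaries and "pilot testing of the intervention, study recruitment, screening, consenting, enrollment, and mailing systems". For the second category, "Implementation costs will include recruitment, salary and fringe benefits for an intervention coordinator", followed by kits, laboratory testing, data management, clinical costs and "drug costs (not paid by the study"). No price source is given for the drug.

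For the comparator, the same section says that "Costing analysis for the standard of care arm within the cost-effectiveness analysis will be based on secondary literature". It cites two PrEP cost-effectiveness analyses, which the reference list dates to 2012 and 2009 (references 7 and 40).

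Section 9.6.1 also describes data that look trial-based: "self-reported time participants spend adhering to the PrEP@Home intervention or standard of care"; hours multiplied by Bureau of Labor Statistics wage rates to give an average standard-of-care cost per man; prescription receipt data; and tracking of costs "during the 12 months of implementation (the time period of the analysis"). The section does not say whose hours these are, or which arm is tracked.

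Section 9.6.3 defines the ICER numerator as intervention cost minus standard-of-care cost, with a bootstrap confidence interval. It gives T = $330,000 and Q = 5.83 per infection averted, and an example threshold of $100,000 per QALY. It plans one-way sensitivity analyses on all inputs, and scenarios that include "the impact of generic drug pricing, one of the major determinants of PrEP cost-effectiveness". The only adjustment of costs over time in Section 9.6 is 3% annual discounting.

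**The concern.** An incremental cost is interpretable only if both arms are priced on the same basis. Here both arms start PrEP before randomization, with the same baseline procedures and the same navigation services (Sections 5.2 and 6.2). Drug price should therefore cancel from the numerator, except through differences in persistence or in which of the two permitted products is prescribed. Nothing in Section 9.6 ensures that it does.

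The same holds for the price of a laboratory test or a clinician hour, and for items counted in one arm only. Recruitment is itemized on the intervention side, and the plan does not mention a matching standard-of-care item.

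At stake is the Aim 3 conclusion: whether PrEP@Home is called cost-saving, cost-effective or neither. The primary outcome is not affected.

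**Working it through.** The documents state no arm cost, incremental cost or ICER, so there is no figure to reproduce. The check has three parts.

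**1. Cost items side by side (Section 9.6.1)**

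| Item | Intervention | Standard of care |
|---|---|---|
| Drug | Listed; price source not stated | Not itemized; may be within the literature costs |
| Recruitment | Listed under both cost categories | Not stated |
| Screening, consenting, enrollment | Developmental costs only | Not stated |
| Personnel | Coordinator salary, clinical costs | Hours x wage rate; source of hours not stated |
| Participant time | Self-report | Self-report |
| Price year | Not stated | Not stated |

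Only participant time is clearly measured the same way in both arms.

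**2. What a price mismatch does**

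Let m_I and m_C be filled months in the intervention and control arms, and p_I and p_C the drug prices used for each.

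Drug increment = p_I m_I - p_C m_C = p_I (m_I - m_C) + (p_I - p_C) m_C.

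The first term is the effect of persistence. The second is purely a source term and vanishes under a common price. If a generic-price scenario lowers the price by g in the intervention arm only, the increment falls by g m_I. With a common price it falls by g (m_I - m_C). The excess, g m_C, is an artificial saving.

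**3. How a mismatch reaches the decision**

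Let d be the part of the per-person-year cost difference due only to source or scope, and a the infections averted per person-year. Neither is in the documents. If C in Section 9.6.3 is incremental cost, which the plan does not state:

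- shift in ICER = d / a
- shift in cost per QALY = d / (Q a)
- cost-saving limit = T = $330,000 per infection averted
- cost-effective limit = T + 100,000 x Q = 330,000 + 583,000 = $913,000 per infection averted
- d that spans the gap between the limits = 583,000 x a

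With an assumed d of $1,000 per person-year and assumed values of a:

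| a per person-year | ICER shift | Shift per QALY | d spanning the gap |
|---|---|---|---|
| 0.001 | $1,000,000 | about $171,500 | $583 |
| 0.005 (1 per 200) | $200,000 | about $34,300 | $2,915 |
| 0.01 (1 per 100) | $100,000 | about $17,200 | $5,830 |
| 0.02 | $50,000 | about $8,600 | $11,660 |

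For example, 1,000 / (5.83 x 0.01) = 17,153 and 1,000 / (5.83 x 0.005) = 34,305. Depending on d and a, the mismatch could be decisive or minor.

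**The case against.** The strongest reply is that the standard-of-care arm is not costed from literature alone. Section 9.6.1 refers to its participant time, to wage-based personnel cost and to prescription data, and Section 6.3 seeks pharmacy fill dates and quantities in both arms. Controls attend outside clinics or a preferred provider (Sections 5.1 and 6.1.1), so study accounts may not capture their care, and literature is a practical source. One-way sensitivity analyses and generic-price scenarios are planned.

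Much of this stands. It means that the trial already plans to collect part of what a common costing needs. It does not close the gap, because the section never says which standard-of-care components come from which source. Varying inputs one at a time does not put the arms on a common basis. Discounting is not price adjustment. A bootstrap of trial data carries no sampling uncertainty for a cost taken from literature.

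On research costs, a reader might infer that screening and consenting are charged to PrEP@Home in the ICER. The plan does not say so. They appear only under developmental costs, whose wording can be read as the cost of piloting those systems, and the plan does not state that developmental costs enter the ICER. Recruitment under implementation could be programme outreach, since Section 9.6 also reports a cost per person contacted. Against that, Section 9.6.3 calls C total costs without excluding either category, so the scope needs stating.

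**Conclusion.** The concern holds in a limited form. The stated method can put differences in source, price and scope into the ICER numerator, and nothing in Section 9.6 prevents it. The size cannot be computed. The figures of about $17,000 and $34,000 per QALY are illustrations that rest on an assumed $1,000 mismatch, assumed infections averted, and C being incremental.

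Three stronger readings are not supported:

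- **That the ICER reflects the cost source as much as the intervention.** This is a statement of size, and the documents give neither d nor a.
- **That the comparator prices are out of date by a known amount.** 2012 and 2009 are publication years. The price years and drug prices in those analyses are not in the documents, nor is any statement on updating them.
- **That 12-month intervention cost is understated.** Participants enrolled after May 2022 are followed for 6 months (Sections 3.1 and 6.3), and Section 9.6.1 has no scaling rule. But nothing says that costs will be left unscaled, Section 9.6.2 expresses effect per unit of person-time, and the share enrolled late is not given.

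The change should be made. It concerns a secondary aim and is inexpensive.

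**What to change.** Amend Sections 9.6.1 and 9.6.3 as follows.

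- Apply one set of unit prices (drug, laboratory test, clinician hour, participant hour) in one stated price year to both arms. In the generic-price scenarios, vary drug price in both arms together.
- Take quantities by arm from trial data where collected, such as prescription fills and self-reported time. Use literature only for standard-of-care quantities that the trial does not capture, and list them. Identify the source of the hours in the personnel calculation.
- Keep the literature totals as a sensitivity analysis.
- Exclude research-only costs (study recruitment, screening, consenting) from the base-case ICER and report developmental costs separately. State whether C is incremental.
- Express recurring costs per person-month, so that 6-month and 12-month participants are on the same 12-month basis.

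Most of this is analysis-plan wording. The downside is that control-arm use would rest on self-report and on pharmacy data that are incomplete, because the release form is optional (Section 6.3). A range for control-arm quantities is therefore needed. The survey domains listed in Section 6.5.1 do not include clinic-visit counts. If these are not collected elsewhere, they need an added survey item or must be named as a literature-based quantity.
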